The parents/legal guardians will be given an explanation about the study and informed consent and/or assent will be obtained. This may occur in the inpatient or the outpatient setting. Demographic information and relevant medical history, including results of scans and thrombophilia testing will be collected. All medications, including anticoagulant medication received for the thrombotic event will be recorded.

a. Baseline Assessments (collected as SOC (standard of care)):

i. History and Physical Examination:

1. Detailed history regarding medical disorders predisposing to thrombosis and potential triggers (birth control pills, recent travel or surgery or immobility) and predispositions (thrombophilia, obesity etc.) will be collected.
2. Review of existing medical records recorded on Children's Medical Center electronic medical record to review past medical, family and social history will be performed.
3. Comprehensive physical exam (PE) consisting of vital signs, general appearance, head, eyes,

ears, nose, throat (HEENT), cardio-respiratory, abdominal, extremities and skin will be performed at each visit as per standard of care.

- ii. Laboratory:
 - 1. Complete blood count (CBC), reticulocyte count, baseline coagulation studies, and a comprehensive thrombophilia panel performed as SOC will be recorded.
- iii. Treatment:
 - 1. Information on anticoagulant therapy (medication of choice, intensity of anticoagulation, planned duration of therapy) prescribed as per the treating physician will be collected for subjects who meet eligibility criteria and whose parents provide written informed consent
- iv. Radiological:
 - 1. All information related to site, extent and venous segments involved of the thrombotic venous segment at the time of diagnosis, and at completion of therapy will be collected. Information on reflux assessment at the time of end of therapy ultrasound will also be collected.
- v. Assessment of **Post-thrombotic syndrome (PTS)**: All subjects will be assessed with standardized, validated outcome assessment tools: the Manco-Johnson Instrument and the modified Villalta scale starting at 6 months post diagnosis of DVT as per standard of care. See appendix 1 for these scales.

b. Study Interventions:

i. Study procedures/Randomization:

Eligible, consenting subjects will be individually randomized via a web-based program to the Fitbit arm or the control arm (1:1 allocation ratio).

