Subjects will be asked to maintain the target steps/day for a period of 8 weeks. At the end of this period, subjects will either maintain the increased activity or resume habitual activity for another 4 weeks, per patient preference. A phone call will be made periodically for encouragement and to ensure adherence to the activity regimen throughout the initial 16-week period. Subjects will have another visit 8 weeks (± 4 weeks) after the end of the 16-week period corresponding to the ~ 9 month post-diagnosis SOC visit. For subjects having difficulty with the activity prescription or use of the Fitbit, a phone call or face-to-face session will be arranged with the study research coordinator and physical therapist. Such changes will be carefully documented.

2. **Control arm.** The control intervention will consist of:
 - 1) a standardized 15-20 minute education session on PTS (what constitutes PTS, why patients get it, how to manage it) and benefits of enhanced activity

(activity will not be specifically addressed and will be up to the choice of the subject) after DVT; 2) monthly phone contacts will be made to check in with patients/families and remind them about completion of activity logs and follow-up visits.

Study assessments for both arms

1. Biomarker testing: Blood for biomarker of coagulation activation (D-dimer, FVIII, thrombin generation), markers of inflammation (CRP), and markers of fibrinolysis {modified thromboelastogram (TEG) with fibrinolysis, PAI-1, will be obtained at each visit One and a half extra teaspoons will be collected at each visit for a total of 4.5 teaspoons collected during the subject's time in the study.}
2. Elastic compression stockings (ECS)
 - i. Subjects in both arms will be provided with custom fitted compression stockings and their use will be tracked using ECS logs throughout study period. In general, SOC recommendations are to wear ECS starting after the diagnosis of DVT and to continue as long as they provide benefit in regards to pain and swelling, up to a period of two years post DVT diagnosis. For the sake of the study, their use will be documented strictly during the study period.
3. Activity log completion during the intervention period will be used to record physical activities. These logs will capture information on the type of activity, and the frequency and duration of activity

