4. Quality of life (all visits): QoL will be measured using the PedsQL™ which is a modular approach to measure generic health related quality of life in both healthy children and adolescents, as well as those with acute and chronic health conditions. It consists of structured interview with the parents and the child with 23 items divided among 4 sub-scales to assess function in 4 domains: Physical; Emotional; social; and School. The instrument is brief, takes 15

minutes to administer, and is developmentally adjusted for a broad age range.

5. PTS : Modified Villalta's scale and Marilyn-Manco Johnson Instruments, the two validated PTS scales, will be used to diagnose and grade severity of PTS at the 6 month mark corresponding to Visit 2 and the 9 month mark (corresponding to Visit 3). The principal and co-investigators will complete PTS evaluations as is standard of care at Visit 2 and Visit 3. In addition, a blinded PTS assessment will also be completed by the physical therapist (currently routinely assigned to the Thrombosis and Bleeding Disorders Program) at both visits.
6. Medication adherence: Anti-Xa and INR will be collected for participants on lovenox and warfarin, respectively. Families with participants on Rivaroxaban will be asked to complete a medication log because no assay will be used to measure adherence for Rivaroxaban. The medication log will measure compliance with anticoagulation during active treatment period and will include the subject's specific anticoagulant, dose, and date and time medication was taken.

See appendix for copies of above questionnaires, administration and scoring procedures.

IV. PARTICIPANT TIMELINE

All study visits will coincide with standard-of-care visits for patients with VTE at our center. All visits will be allowed a time window to accommodate preferences of subjects and families \pm 2 weeks for visit 1 and \pm 4 weeks for visit 2 and 3.

Study assessments: (Table 1 for schedule of events).

V. MODIFICATIONS

a. RISKS

- i. Blood Draws: Risks associated with drawing blood include minimal discomfort and/or bruising, infection,

- excess bleeding, clotting, and/or fainting are possible.
- ii. Doppler Ultrasound: There are no risks from the sound waves used for ultrasound. The test is not painful and does not have any radiation. This will be done as per standard of care.
- iii. Skin irritation or allergies with wearing the activity tracker
- iv. Injuries or falls related to increased physical activity

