- b. Subjects who need to continue long term prophylactic anticoagulation will still be eligible and will be included at discretion of their attending hematologist.
- c. The activity tracker, the Fitbit, is made up of a flexible durable material used in many sports watches (and one that does not contain latex) with a surgical grade stainless steel clasp and contains traces of nickel. It is meant to be worn day and night on the wrist. Because there's a possibility of skin irritation and allergies with any type of jewelry, all participants in this study will be warned and care and wearing tips will be provided. They will be monitored for any skin problems during the clinic visits and a treatment plan will be made in collaboration with their primary pediatrician should any skin irritation develop. I will ask to be notified immediately of any such occurrence at home and will then contact the participant or the family to assess

their clinical condition and make a treatment plan based on the severity of the skin condition.

VII. OUTCOMES AND POWER CALCULATIONS

Primary Outcomes will be 1) **feasibility indicators (Table 2)** measured throughout trial. The level of adherence in the intervention group will be calculated as the proportion meeting the weekly steps/day goal during the 'active' 8-week period of the total 16 weeks of intervention as determined by the Fitabase data platform output, and 2) **change in clinical outcomes**

such as PTS biomarkers at baseline and Visit 2, and QoL (at all visits). Secondary outcome: I will assess for PTS with validated scales at the 6 and 9 month follow-up visit as is standard of care.

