Analyses: The objectives of this trial are to assess the feasibility of the design and to measure the effect size of the intervention. All analyses will therefore be descriptive and will be performed once, at the end of the trial. Means and standard deviations, or when appropriate, medians and semi-inter-quartile ranges will be used to describe demographic and clinical characteristics. Reasons for non-eligibility, lack of consent, dropout and lack of compliance will be documented. For feasibility indicators, we (study investigators and [name]-biostatistician) will describe rate of eligibility (proportion of subjects screened who fully meet trial eligibility criteria to participate in the trial), rate of consent (the proportion of eligible subjects who consent to participate) and rate of loss to follow-up (proportion of randomized subjects who drop out of the trial, in total, and by allocated intervention). We will also describe the level of compliance in the intervention group, calculated as the ratio of who complied with the activity prescription to the number given the prescription. We will consider the trial *successful* if the following criteria are met: rate of eligibility $\geq 30\%$, rate of consent $\geq 30\%$, rate of loss of follow-up $<20\%$, level of compliance $\geq 60\%$ and proportion of subjects who complete the trial $\geq 80\%$. For the clinical outcomes (including the secondary outcomes), we will describe change (means and standard deviations) in the intervention and control groups, from baseline to 6 month, in the QoL scores and PTS biomarkers. Each change score will be interpreted for clinical significance and common responses counted for frequency of occurrence. The impact of the activity

Table 2: Feasibility Indicators

Proportion of screened subjects who meet eligibility criteria: $\geq 30\%$

Proportion of screened subjects who provide consent: $\geq 30\%$

Level of adherence in the intervention arm: $\geq 60\%$

Proportion of subjects who complete the trial: $\geq 80\%$

tracker to promote continued physical activity in the last 2 weeks of the 12-week period would be explored. We will also assess the impact of covariates such as age, sex, BMI, baseline activity, intensity of activity over and above the activity prescription, on change scores.

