Sample size calculation: For reasons of practicality and cost, we have decided to limit the size of this pilot RCT to 44 subjects (20 in each arm; 22 after considering a 20% drop out rate). We anticipate that the probable primary outcome for the larger trial will be change in rate of PTS development and/or progression. This trial may also provide compelling preliminary data for future studies. For example, if this intervention reduces the risk of PTS from 26% (known probability of PTS) to 10%, this pilot study has 71% chance of showing a promising trend (p-value<0.2) that the intervention reduces the risk of PTS. We acknowledge that the small size of this pilot study limits the validity of the findings; therefore, we will be cautious with such analyses.

I. RECRUITMENT

- a. Information about the clinical study will be provided via direct communication by study investigators and physicians at Children's Medical Center including ED physicians, hospitalists, and general pediatricians attending on the inpatient medicine services and outpatient continuity clinic as well as house officers.
- b. Information regarding the study will be available on the University of Texas Southwestern clinical trials website and at clinicaltrials.gov.
- c. Potential subjects will be identified through review of new patient referrals to Children's Medical Center, inpatient admissions and/or consultations for thrombosis.
- d. Each subject will receive financial compensation for participation. Payment will be made at completion of the study visits at Visits 1 and 2 (\$25 each) and at the end of Visit 3 (\$50) based on attendance and return of the tracking logs.
- e. Expected recruitment rate will be 2-3 participants per month.
- f. Duration of recruitment period is expected to be approximately 24 months.

- g. Assessment of study recruitment and retention will be performed when 20 participants have been enrolled on the study, or at approximately 9 -12 months.

II. DATA COLLECTION, MANAGEMENT AND ANALYSIS

a. DATA COLLECTION METHODS

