using mean (standard deviations [SD]) for continuous outcomes, and raw counts (%) for categorical outcomes are reported. For the clinical end points, using an intent-to-treat analysis that includes all participants with data at baseline and 6 months (end of the intervention period), within-patient change from baseline (diagnosis or pre-VTE levels) to 6 months (mean, SD) in the physical activity will be compared to standard care in the following measures: D-dimer, FVIII, CRP, thrombin generation assay parameters of endogenous thrombin potential and peak thrombin, fibrinolysis on thromboelastography, QoL (total and physical), selfreported physical activity levels, and PTS (change from 6 to 9 months). This will be averaged for each group, and within-group differences will be compared between the standard care and physical activity groups using a t test. ECS use will be descriptively described but not included in a formal analysis.

ETHICS AND DISSEMINATION

I. RESEARCH ETHICS APPROVAL

This protocol and template informed consent forms will be reviewed and approved UT Southwestern IRB with respect to scientific content and compliance with applicable research and human subjects regulations. Subsequent to initial review and approval, the investigators will submit progress reports to the IRB at least annually and at study closure.

II. PROTOCOL AMMENDMENTS

Any modifications to the protocol, which impact the conduct of the study, or potential risk/benefit of the participants, will require a formal amendment to the protocol with IRB approval.

III. CONSENT OR ASSENT

Informed consent will be obtained after information has been provided to patients' families along with a discussion of the risks and benefits along with opportunity for questions. Consent forms will be provided for all parents involved in the trial.

IV. CONFIDENTIALITY

Records of each patient's participation in this study, including the original informed consent document, will be kept in a locked file cabinet in the Center for Cancer and Blood Disorders at Children's Medical Center. Access to local

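### The only planned PTS comparison is a t test on change from 6 to 9 months, which does not test the 26% versus 10% risk reduction quoted in the sample-size paragraph; no comparison of PTS risk between arms is written

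*Combined protocol and SAP*

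**What the plan says.** - **When PTS is measured.** The baseline-assessments section has PTS scored "starting at 6 months post diagnosis of DVT as per standard of care". Table 1 has no PTS assessment at Visit 1, only at Visits 2 and 3. The outcomes section makes PTS the secondary outcome: "I will assess for PTS with validated scales at the 6 and 9 month follow-up visit".
- **How the visits relate to the regimen.** Section c describes the follow-up point as "6 months (end of the intervention period"). The intervention-arm schedule then says "Subjects will have another visit 8 weeks (± 4 weeks) after the end of the 16-week period", which is Visit 3.
- **The written PTS analysis.** Section c lists "selfreported physical activity levels, and PTS (change from 6 to 9 months") among the within-patient changes that are averaged per arm and compared by t test. It does not say whether PTS enters as a score or as a diagnosis. Under the study assessments, the two scales "will be used to diagnose and grade severity of PTS at the 6 month mark" and again at 9 months, so both readings are open.
- **The quoted chance of success.** The sample-size paragraph says "if this intervention reduces the risk of PTS from 26% (known probability of PTS) to 10%, this pilot study has 71% chance" of a promising trend, defined as p<0.2. It gives no test, sidedness, visit or scale.
- **The general analysis text.** "For the clinical outcomes (including the secondary outcomes), we will describe change (means and standard deviations) in the intervention and control groups". The change meant there starts at the baseline visit, ends at 6 months, and covers QoL scores and PTS biomarkers.

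**The concern.** The sample-size paragraph concerns how many patients in each arm have PTS. The analysis section concerns how PTS moves between two visits that both follow the 16-week regimen. If the regimen prevents PTS while it is being followed, the benefit is already in the Visit 2 score, and a change score starting at Visit 2 removes it.

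Nothing else in the plan fills the gap. The general analysis text covers change from baseline, but PTS has no baseline score. Counts and percentages are planned for the feasibility outcomes only.

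PTS is the secondary outcome, and the sponsor expects PTS development or progression to be the primary outcome of the larger trial. The pilot could therefore hand that trial a PTS result that shows nothing, or points towards harm, although the Fitbit arm had less PTS at both visits.

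**Working it through.** **1. The plan's 71%.** Inputs, all from the sample-size paragraph: control risk 0.26, Fitbit risk 0.10, threshold 0.2, and 20 per arm (22 before dropout). Allocation is 1:1. For two proportions with pooled variance under the null:

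power = Φ[(δ − z·SE0)/SE1], with δ = 0.26 − 0.10 = 0.16, SE0 = √(2 × 0.18 × 0.82/n), SE1 = √((0.26 × 0.74 + 0.10 × 0.90)/n)

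| n per arm | SE0 | SE1 | One-sided (z = 0.8416) | Two-sided (z = 1.2816) |
|---|---|---|---|---|
| 22 | 0.1158 | 0.1133 | Φ(0.552) = 70.9% | Φ(0.102) = 54.1% |
| 20 | 0.1215 | 0.1188 | Φ(0.486) = 68.7% | Φ(0.036) = 51.4% |

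Exact enumeration of the one-sided pooled z test gives 72.6% (22 per arm) and 70.7% (20 per arm). The 71% is thus a one-sided, uncorrected comparison of two proportions. It does not identify the per-arm number: 22 by normal approximation and 20 by exact calculation both round to 71%.

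**2. What the written t test estimates.** Let C2, C3 be the control mean (or risk) at Visits 2 and 3, and F2, F3 the same for the Fitbit arm. The change contrast is

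(F3 − F2) − (C3 − C2) = (F3 − C3) − (F2 − C2)

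This is the arm difference at Visit 3 minus the arm difference at Visit 2. A difference that is equal at both visits gives zero. This holds for a score and for a diagnosis.

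**3. Size, by illustration.** The documents give neither the time course nor the persistence of PTS, so these are assumptions: PTS coded 0/1; 10%, 20% or 30% of Visit 2 cases remit by Visit 3; the new-case rate is set to reach the stated Visit 3 risk; 20 or 22 per arm; one-sided p<0.2. The change test was simulated with a pooled t test (200,000 trials per setting). The tests of proportions were enumerated exactly.

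| Control risk, Visit 2 → 3 | Fitbit risk, Visit 2 → 3 | Change test favourable | Change test unfavourable | Proportions at Visit 2, favourable | Proportions at Visit 3, favourable |
|---|---|---|---|---|---|
| 26% → 26% | 10% → 10% | 21-27% | 21-27% | 71-73% | 71-73% |
| 13% → 26% | 5% → 10% | 44-53% | 5-7% | 57-59% | 71-73% |
| 26% → 26% | 10% → 18% | 5-7% | 42-61% | 71-73% | 41-42% |
| 10% → 26% | 10% → 10% | 73-88% | about 1% | no true difference | 71-73% |

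The true change contrasts are 0, −8, +8 and −16 percentage points. In the third row the Fitbit arm has less PTS at both visits, yet the change contrast points the other way.

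**4. The same question with no remission.** Suppose PTS never resolves, the 9-month risks are 26% and 10%, and a share of that PTS is already present at 6 months (20 per arm, one-sided 0.2). The chance that the change test is favourable is then about 71% if the share is none, 64% if a quarter, 58% if a half, 49% if three quarters, and 0% if all of it, because then nobody changes.

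**The case against.** The strongest reply is that the 71% carries little weight in the design. The number of patients was fixed on practical and cost grounds, the 71% is offered as an example, and the sponsor promises caution. Analyses are called descriptive and success is judged on feasibility. All of that stands: the mismatch undermines neither the sample size nor the success decision. But a descriptive plan still has to name what it will estimate, and the only PTS estimate named is the 6-to-9-month change.

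Second, the outcome foreseen for the larger trial includes progression as well as development, and a change score bears on progression. Also, Table 1 has the Fitbit returned only at Visit 3, so an effect may continue after Visit 2. This stands too: the change score is a legitimate measure of progression or durability, and the fourth scenario shows it can see a late effect. What is missing is development up to Visit 2.

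Third, the directional wording in the sample-size paragraph suggests a one-sided reading. That is fair, but two-sided the figure would be 54.1% or 51.4%, so it should be said outright.

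Fourth, the scenarios assume a 0/1 outcome, remission rates and timing that the documents do not give, and no score-based scenario is shown. That limits the percentages. It does not touch the algebra in step 2. In the third scenario the test also reports its own quantity correctly; the danger is that change read without the visit-level proportions would be taken as harm.

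**Conclusion.** The concern holds and should be fixed. The only PTS comparison written measures change after the point that section c calls the end of the intervention, and the risk contrast behind the 71% has no planned analysis.

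That the Visit 2 difference is subtracted out follows from the plan's own text. How much is lost depends on when an effect arises and how long PTS lasts, which the documents do not state. Under the assumptions shown, the change test is favourable in anything from 5-7% to 73-88% of trials. With a constant 26% versus 10% it cannot tell the arms apart.

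The consequence is confined to the preliminary PTS estimate for the larger trial.

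**What to change.** In section c (Statistical Analyses):

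- Compare the proportion with PTS, and the scale score, between arms at Visit 2 and at Visit 3. Report the risk difference with a confidence interval.
- State whether PTS is analysed as a diagnosis or a score, on which of the two scales, and what counts as PTS present.
- Keep the 6-to-9-month change as a supplementary description of progression or durability, shown beside the visit-level results.

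In the sample-size paragraph, state that the 71% is one-sided, and name the test and per-arm number behind it. By normal approximation it is 70.9% with 22 and 68.7% with 20; by exact calculation 72.6% and 70.7%. Since 22 is the number before dropout, say which number is meant.

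The cost is a few sentences in the statistical section and one clause in the sample-size paragraph. PTS is already scored at both visits, so no visit, assessment or patient is added.

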- 1. **Intervention (Fitbit) arm.** The intervention arm will wear a Fitbit for a 16-week period (**Figure 2**). **General Principles of an aerobic activity regimen:**

As the principal muscles affected by PTS are the lower limb muscles, we have opted to use a walking-jogging program to capture steps/day by the Fitbit. This will target all potentially affected muscles (quadriceps, hamstrings and gastrocnemius/soleus). If preferred by the subject, other weight bearing exercises could replace the walk/jog, for example, dancing or team sports such as basketball or volleyball. Because of the unfamiliarity with activity trackers, subjects will be provided with hands-on training to promote successful use of the Fitbit and Fitabase.

a. Schedule and procedures (Table 1): After consent (baseline visit), subjects in this arm will receive a standardized 15-20 minute education session on PTS (what constitutes PTS, why patients get it, how to manage it) and enhanced activity after DVT. Subjects will be asked to wear the Fitbit for a period of four weeks to establish baseline or 'habitual' activity. Using steps/day data received at the end of four weeks, we will determine an individualized activity prescription of 'target steps/day', corresponding to a 25% increase above the baseline.

Table 1	Visit 1	Visit 2	Visit 3
	12 wks post DVT Dx (\pm 2 weeks)	16 wks after Visit 1 (\pm 4 weeks)	8 wks after Visit 2 (\pm 4 weeks)
	SOC Visit	SOC Visit	SOC Visit (Exit Visit)
ALL SUBJECTS			
Informed Consent	X*		
Full Medical History and Exam	X	X	
Biomarker Testing [^]	X\$	X	X
FXIII, D-dimer, CRP	X	X	X ^{^^}
QOL forms	X	X	X
PTS Assessment		X	X
ECS and Log	X	X~	X~
Activity Logs/ Questionnaire	X	X	X
Medication Log***	X	X	X

Phone Calls (monthly)	X	X	
Formal Education Session	X		
Honoraria**	X	X	X
SUBJECTS IN FITBIT ARM			
Hands on Fitbit Training	X		
Steps/Day Data (weekly)	X	X	X
Phone Calls (weekly)	X	X	
Return Fitbit			X

*Informed consent can occur any time after DVT diagnosis until Visit 1; ^Biomarker testing includes: D-Dimer, FVIII, Thrombin generation, markers of fibrinolysis; \$Biomarker testing at Visit 1 may be combined with other SOC labs for those still on anticoagulation at this time; ~ only ECS logs; ** \$25 at Visit 1 and 2, and \$50 at Visit 3; ***Medication logs only for participants on Rivaroxaban or Xarelto; ^^Factor VIII, D-dimer, and CRP can be completed as research procedures at Visit 3 for participant's whose values were within normal range at Visit 2.

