1. During a typical **7-Day period** (a week), how many times on the average do you do the following kinds of exercise for **more than 15 minutes** during your free time (write on each line the appropriate number).

	Times Per Week
a) STRENUOUS EXERCISE (HEART BEATS RAPIDLY) (e.g., running, jogging, hockey, football, soccer, squash, basketball, cross country skiing, judo, roller skating, vigorous swimming, vigorous long distance bicycling)	
b) MODERATE EXERCISE (NOT EXHAUSTING) (e.g., fast walking, baseball, tennis, easy bicycling, volleyball, badminton, easy swimming, alpine skiing, popular and folk dancing)	
c) MILD EXERCISE (MINIMAL EFFORT) (e.g., yoga, archery, fishing from river bank, bowling, horseshoes, golf, snow-mobiling, easy walking)	

2. During a typical **7-Day period** (a week), in your leisure time, how often do you engage in any regular activity **long enough to work up a sweat** (heart beats rapidly)?

OFTEN

SOMETIMES

NEVER/RARELY

1. 

2. 

3. 

Thank you for your patience. You are almost done.

-----For Research Use:

1. Time taken to complete survey (minutes): _____

2. Subject's Habitual Physical Activity (i.e before the diagnosis of DVT):

- Mild (gardening, yoga, archery, fishing, bowling, golf, walking, swimming, snow mobiling)
- Moderate (dancing, baseball, bicycling, volleyball, badminton, cross-country skiing, skating)
- Strenuous (tennis, running, jogging, hockey, football, soccer, squash, basketball, alpine skiing, judo)
- Mostly Inactive

*If a subject has participated in activities qualifying for more than 1 intensity category, classify in the highest category

3. Godin Score before the diagnosis of VTE:

4. PAQ-C/ PAQ-A Score before the diagnosis of VTE:

5. Subject's Physical Activity as assessed at the current visit:

None

- Mild (gardening, yoga, archery, fishing, bowling, golf, walking, swimming, snowmobiling)
- Moderate (dancing, baseball, bicycling, volleyball, badminton, cross-country skiing, skating)
- Strenuous (tennis, running, jogging, hockey, football, soccer, squash, basketball, alpine skiing, judo)
- Mostly Inactive

6. Godin Score after the diagnosis of VTE:

7. PAQ-C/ PAQ-A Score before the diagnosis of VTE:

8. Other comments:

Godin Leisure-Time Exercise Questionnaire

3. During a typical **7-Day period** (a week), how many times on the average do you do the following kinds of exercise for **more than 15 minutes** during your free time (write on each line the appropriate number).

	Times
	Per
	Week

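### Biomarkers, PedsQL and self-reported activity are compared by an unadjusted t test on change from an unclear baseline; ANCOVA on the scheduled Visit 1 value would usually be more precise

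*Combined protocol and SAP*

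**What the plan says.** Section II.c (Statistical Analyses) takes participants with data at baseline and 6 months, computes each one's change, and then: "within-group differences will be compared between the standard care and physical activity groups using a t test". The measures are D-dimer, FVIII, CRP, thrombin generation, fibrinolysis on thromboelastography, QoL and self-reported activity. PTS is also listed, as change from 6 to 9 months. No covariate is named for this comparison.

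The change is defined as "within-patient change from baseline (diagnosis or pre-VTE levels) to 6 months (mean, SD".

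Table 1 marks biomarkers, QoL forms and the activity questionnaire at Visit 1, and its footnote allows that "Biomarker testing at Visit 1 may be combined with other SOC labs" for those still on anticoagulation. The section on assessments for both arms also places biomarkers and PedsQL at every visit.

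Section VII (Outcomes and Power Calculations) puts change in clinical outcomes among the primary outcomes: "such as PTS biomarkers at baseline and Visit 2, and QoL (at all visits". Its Analyses paragraph states: "The objectives of this trial are to assess the feasibility of the design and to measure the effect size of the intervention". It adds: "We will also assess the impact of covariates such as age, sex, BMI, baseline activity", together with activity intensity, in relation to change scores. No model is given, and the biomarkers' and PedsQL's own baseline values are not listed.

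**The concern.** There are two linked problems.

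**The baseline is not settled.** The analysis section points to diagnosis or the time before the clot. Table 1 schedules no research biomarker or PedsQL before Visit 1, and Section III calls the consent visit the baseline visit. Section III does record standard-of-care laboratory results, but it does not say that they include the analysed biomarkers. The only pre-clot score on the forms is for activity (Appendix 5, "Godin Score before the diagnosis of VTE" and the matching PAQ item). Read literally, the change would span about 12 weeks before the activity regimen starts and would need values the schedule does not supply. Two analysts could compute different effects from the same data.

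**The comparison is less precise than it could be.** A change score subtracts the whole baseline, whatever its correlation with follow-up. ANCOVA estimates how much to subtract. With about 35 to 44 evaluable subjects and an objective of measuring an effect size, the unused precision matters. The change score also leaves a fraction (1 − rho) of any chance Visit 1 imbalance in the estimate.

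**Working it through.** **Plan's own figure.** The plan gives no precision or power figure for these measures. Its only power figure is 71% for PTS at 26% versus 10% with p<0.2. That reproduces as a one-sided test with 22 per arm (70.9%, pooled normal approximation), and nothing below depends on it.

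**Inputs from the documents.** 1:1 allocation; 20 per arm, 22 with the dropout allowance (Sample size calculation). So N = 40 as planned, N = 44 with no loss, and 44 × 0.8 ≈ 35 if 20% drop out.

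**Assumptions.** Rho between Visit 1 and Visit 2 is not given, so I use 0.3 to 0.9. SDs are first taken as equal at both visits.

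**Formulae (SD = 1).**
- Change-score variance: 2(1 − rho).
- ANCOVA residual variance: 1 − rho².
- Ratio: (1 + rho)/2, times 1 + 1/(N − 4) for estimating one slope. At N = 40 this factor is 1 + 1/36 = 1.0278.
- 95% CI half-width: t × √(variance × 2/20), with t = 2.024 (38 df) or 2.026 (37 df). The ANCOVA variance includes the factor 1.0278.

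| rho | (1+rho)/2 | × 1.0278 | 40 ÷ ratio | Half-width, change (SD) | Half-width, ANCOVA (SD) |
|---|---|---|---|---|---|
| 0.3 | 0.65 | 0.668 | 59.9 | 0.76 | 0.62 |
| 0.5 | 0.75 | 0.771 | 51.9 | 0.64 | 0.56 |
| 0.7 | 0.85 | 0.874 | 45.8 | 0.50 | 0.46 |
| 0.9 | 0.95 | 0.976 | 41.0 | 0.29 | 0.28 |

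A simulation of 100,000 trials with 20 per arm gave ratios of 0.666, 0.774, 0.874 and 0.977. A smaller one (4,000 trials per rho) showed type I error near 5% for both methods.

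**Other sample sizes.** N = 35 (factor 1.0323): 0.671, 0.774, 0.877, 0.981. N = 44 (factor 1.025): 0.666, 0.769, 0.871, 0.974.

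**Break-even with equal SDs.** (1 + rho)/2 × 1.0278 = 1 gives rho = 2/1.0278 − 1 = 0.946.

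**Against ignoring baseline altogether.** Change-score variance relative to comparing Visit 2 values alone is 2(1 − rho): 1.4 at rho 0.3, 1.0 at 0.5, 0.6 at 0.7. Below rho 0.5 the planned analysis is less precise than using no baseline.

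**Chance imbalance.** The SE of the Visit 1 difference is √(2/20) = 0.316 SD. P(|gap| > 0.3 SD) = 2 × (1 − Φ(0.949)) = 0.343. A 0.3 SD gap shifts the change contrast by (1 − rho) × 0.3, which is 0.21, 0.15, 0.09 or 0.03 SD at the four rho values.

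**Unequal SDs.** With s1 and s2 the SDs at Visits 1 and 2, change-score variance minus ANCOVA residual variance is

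s1² + s2² − 2·rho·s1·s2 − s2²(1 − rho²) = (s1 − rho·s2)² ≥ 0.

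ANCOVA can therefore lose only the slope-estimation factor, about 3% at N = 40. With k = s2/s1, the ratio is 1.0278(1 − rho²)/(1 + 1/k² − 2·rho/k). At k = 0.7 it is 0.43, 0.48, 0.50, 0.42. At k = 1.43 it is 0.87, 0.98, 1.03, 0.85. The range is 0.42 to 1.03.

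**The case against.** The strongest reply is that this is a preference about efficiency. The change-score t test is valid, the plan calls its analyses descriptive and promises caution, and no success criterion rests on these comparisons. The sample size section says that "the probable primary outcome for the larger trial will be change in rate of PTS development and/or progression", so these measures are not expected to drive the next trial. The Primary Aim frames the effect-size outcome as change within each group, and ANCOVA does not sharpen those summaries. The covariate list is open-ended, and regressing change on its own baseline plus arm gives the same arm effect as ANCOVA. Finally, the gain depends on a correlation nobody has stated, and the imbalance argument is largely the same inefficiency seen from another side.

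Most of this is true and limits the point:
- It is not a bias, and only the between-arm contrast benefits.
- At rho 0.7 or above the interval narrows little.
- For self-reported activity, baseline activity may already be meant as the covariate.
- A pre-clot reference for activity may be deliberate, since the form collects it.

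It does not dispose of the point. The plan specifies a between-arm test and makes effect size an objective, so the contrast should be estimated as well as the data allow. The covariate sentence gives no model and leaves out the biomarkers' and PedsQL's own baselines. The baseline inconsistency does not depend on rho at all.

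**Conclusion.** The concern holds, as an improvement that should be made rather than an error of validity. The planned test ignores the correlation between Visit 1 and Visit 2, although the Visit 1 values are already scheduled. With equal SDs and 20 evaluable per arm, ANCOVA removes about 33%, 23%, 13% or 2% of the variance at rho 0.3, 0.5, 0.7 or 0.9. Its possible loss is capped at about 3% under the usual linear model. The size of the gain rests on rho and the SD ratio, neither of which is in the documents, and on Visit 1 being the intended baseline. If diagnosis values were meant, the figures would refer to a different pair of time points. PTS lies outside the finding because it is first scored at Visit 2 and has no pre-intervention value to adjust for.

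**What to change.** 1. Reconcile the baseline wording in Statistical Analyses with Table 1 by naming the Visit 1 value as baseline for the biomarkers, PedsQL and current self-reported activity.
2. For each of these, estimate the between-arm difference at Visit 2 by ANCOVA with arm and that outcome's own Visit 1 value, and report it with a 95% CI.
3. Keep the within-group mean changes and SDs as descriptive summaries.
4. If D-dimer or CRP prove right-skewed (an assumption, as the documents give no distributions), analyse them on the log scale and report geometric-mean ratios.
5. Leave PTS out of this model.

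The cost is one definition to settle, a few lines of analysis text and little programming, with no new data. The downside is one degree of freedom per model (variance factor 1.03 at 40 subjects) and almost no gain if rho is about 0.9 or higher.
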